6.5 Data Quality Assurance

Report summaries will be generated using validated Base SAS[®] software, version 9.4 or higher, on a PC or server-based platform. Additional validated software may be used to generate analyses, as needed.

All SAS programs that create outputs or supporting analysis datasets will be validated by a second statistical programmer or biostatistician. At a minimum, validation of programs will consist of a review of the program log, review of output or dataset format and structure, and independent confirmatory programming to verify output results or dataset content. Additionally, all outputs will undergo a review by a senior level team member before finalization.

The content of the source data will be reviewed on an ongoing basis by project statistical programmers and statisticians. Data will be checked for missing values, invalid records, and extreme outliers through defensive programming applications, analysis-based edit checks, and other programmatic testing procedures. All findings will be forwarded to the project data manager for appropriate action and resolution.

7 STATISTICAL METHODS

7.1 General Methodology

Data will be analyzed by Precision for Medicine biostatistics personnel. Statistical analyses will be reported with tables, figures, and listings, presented in rich text format, and using recommended ICH numbering. Output specifications for all tables, figures, and listings will be in conformance with guidelines specified by the ICH in Appendix 7 of the *Electronic Common Technical Document Specification* (Apr 2003).

7.1.1 Reporting Conventions

Tables and figures will be summarized by dose cohort. All tables (including efficacy) will also include a column for all subjects combined. In general, all collected data and any derived data will be presented in subject data listings, for all enrolled subjects. Listings will be ordered by dose cohort, site (part of subject number), subject number and assessment or event date.

In general, continuous variables will be summarized to indicate the study population sample size (N), number of subjects with available data (n), mean, SD, median, 25th (Q1) and 75th (Q3) quartiles, minimum, and maximum values, unless otherwise specified. Categorical variables will be summarized by the population size (N), number of subjects with available data (n), number of subjects in each category, and the percentage of subjects in each category. Unless otherwise noted, the denominator to determine the percentage of subjects in each category will be based on the number of subjects with available data. Select ordinal data may be summarized using both descriptive statistics and counts and percentages of subjects in each category, as appropriate.

Non-zero percentages will be rounded to one decimal place. Rounding conventions for presentation of summary statistics will be based on the precision of the variable of summarization, as it is collected in its rawest form (i.e., on the electronic case report form [eCRF] or as provided within an external file) and are outlined as follows:

- The mean and median will be rounded to one more decimal place than the precision of the variable of summarization;
- Measures of variability (e.g., SD, SE) will be rounded to two more decimal places than the precision of the variable of summarization; and
- Minimum and maximum values will be presented using the same precision as the variable of summarization.

Time to event variables will be summarized using the Kaplan-Meier method. Where confidence limits are appropriate, the confidence level will be 95% (two-sided), unless otherwise stated.

7.1.2 *Summarization by Visit*

Data summarized by study visit will be based on the nominal, scheduled visit label as reported on the eCRF.

Data collected at unscheduled visits will not be included in by-visit summaries, but will be considered when endpoint derivations potentially include multiple visits (e.g., determination of baseline value, determination of worst post-baseline value, etc.). All data will be included in subject listings.

7.1.3 *Baseline Value*

For analyses listed in this SAP, the baseline value is defined as the last measurement reported prior to the first infusion of investigational product, unless otherwise noted. Assessments done at the C1D1 visit are performed pre-infusion unless otherwise noted. In cases where there is more than one pre-infusion value, the most recent pre-infusion value will be determined to be the baseline.

7.1.4 *Data Handling Rules*

Unless otherwise noted, values reported as greater than or less than some quantifiable limit (eg, “< 1.0”) will be summarized with the sign suppressed in summary tables and figures, using the numeric value reported. Data will display on subject listings to include the sign.

7.1.5 *Standard Calculations*

Where appropriate, the calculated study day of each assessment or event will be presented with the assessment or event date on subject data listings, where study day will be determined as:

- The assessment/event date minus the date of first infusion, if the assessment/event date is prior to the date of first infusion; and
- The assessment/event date minus the date of first infusion, plus one, if the assessment/event date is on or after the date of first infusion.

Other variables requiring calculations will be derived using the following formulas:

- **Days:** A duration between two dates expressed in days will be calculated as follows:

- Later date – earlier date + 1
- **Months:** A duration expressed in months will be calculated by dividing the duration in days by (365.25 / 12) or 30.4375;
- **Years:** A duration expressed in years will be calculated by dividing the duration in days by 365.25;
- **Change from Baseline:** Change from baseline will be calculated as the post-baseline value minus the baseline value;
- **Percentage Change from Baseline:** Percentage change from baseline will be calculated as the change from baseline divided by the baseline value, multiplied by 100.

7.2 Analysis Populations

The analysis sets are defined as follows:

- Safety analysis set: Includes all subjects who receive at least one infusion of investigational product, including partial infusions.
- Efficacy Evaluable analysis set: Includes all subjects who receive at least one complete infusion of investigational product, have measurable disease at baseline per RECIST v1.1 or modified MDA criteria for bone-exclusive disease and have at least one post-baseline on-study assessment of tumor response (based on local, Investigator read data). This population will be used for the analysis of efficacy data based on local read data and efficacy data which is not dependent on the reader (i.e. overall survival). Baseline summaries will also use this population.
- Efficacy Evaluable analysis set (Central): Includes all subjects who receive at least one complete infusion of investigational product, have measurable disease at baseline per RECIST v1.1 or modified MDA criteria for bone-exclusive disease and have at least one post-baseline on-study assessment of tumor response (based on central read data). This population will be used for the analysis of efficacy data based on central read data only.
- Per-Protocol (PP) analysis set: Includes all efficacy evaluable subjects who have no major protocol deviations as defined by the Sponsor prior to database lock.

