### **Analysis Population**

- Safety analysis set consists of all enrolled patients who received at least one dose of investigational product (even a partial dose).
- Efficacy evaluable set includes all patients who receive investigational product and have at least one post baseline on-study assessment of tumor response.
- Per-protocol (PP) analysis set consists of all efficacy evaluable patients without major protocol deviations, as defined by the Sponsor prior to database lock
- PK analysis set includes all patients who receive investigational product and have at least one post baseline evaluable PK sample.

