### **9.3 ANALYSIS SETS**

The following analysis sets will be used in this study:

- Safety analysis set: All patients who receive at least one dose of investigational product (even a partial dose).
- Efficacy evaluable set: All patients who receive at least one dose of investigational product, have measurable disease at baseline per RECIST v1.1 or modified MDA criteria for bone-exclusive disease (see [Table 11](#)), and have at least one post-baseline on-study assessment of tumor response.
- Per-protocol (PP) analysis set: All efficacy evaluable patients who have no major protocol violations, as defined by the Sponsor prior to database lock.
- PK analysis set includes all patients who receive investigational product and have at least one post baseline evaluable PK sample.

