If both the start day and month of an event are missing, the start day and month will be replaced by the start day and month of study treatment if the event and the start of the treatment occur in the same year; otherwise, it will be replaced by 1st of January. All imputed dates will have to be prior to the dates of withdrawal of consent, lost to followup, and death.

7.5.4.3 *Interim Analyses and Data Monitoring*

Throughout the study, a DMC will monitor safety parameters at regular intervals (approximately quarterly) after at least 3 subjects have been treated for at least 1 cycle. There was no formal interim analysis undertaken. Multicenter Studies

This is a multicenter study. Sites in North America, Europe, and Canada are expected to participate. All data collected from all study centers will be pooled for data analysis.

7.5.4.4 *Multiple Comparisons/Multiplicity*

No adjustments for multiple comparisons will be made. A single primary endpoint has been identified and each cohort is viewed as a separate study. No adjustment among secondary endpoints will be made as this study is exploratory.

7.5.4.5 *Use of an “Efficacy Subset” of Subjects*

The efficacy analysis will be performed on the Efficacy Evaluable analysis set since this population is the subset of the Safety analysis set who have measurable disease at baseline and have at least one post-baseline on-study assessment of tumor response.

The PP analysis set will be utilized as a sensitivity analysis. The PP analysis set will exclude subjects with major protocol violations as determined by the Sponsor prior to database lock.

7.5.4.6 *Active-Control Studies Intended to Show Equivalence*

This study does not include an active-control product and is not intended to demonstrate equivalence between any two drug products.

7.5.4.7 *Examination of Subgroups*

The primary and secondary efficacy endpoints (excluding the QoL data) will be summarized by various subgroups of interest. The subgroups are defined in Section 7.5.2.

Additional subgroup analyses may be performed post-hoc, as appropriate.

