7.10 Changes in the Conduct of the Study or Planned Analyses

Disease control rate and time to response were added as secondary efficacy endpoints to further explore the clinical activity.

There were no other changes to the study conduct or planned analyses identified within the development of this SAP, relative to the descriptions provided within the clinical study protocol.

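### SAP 7.2 adds an undeclared complete-infusion condition to the primary efficacy set, and the central-read repeat of the primary analysis uses its own denominator

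*SAP*

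**What the plan says.** **Exposure condition.** Protocol 9.3 defines the Efficacy Evaluable set as "All patients who receive at least one dose of investigational product, have measurable disease at baseline per RECIST v1.1" (or the modified MDA criteria), plus a post-baseline tumour assessment. The synopsis asks for receipt of product and that patients "have at least one post baseline on-study assessment of tumor response". Neither mentions completeness.

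SAP 7.2 instead says "Includes all subjects who receive at least one complete infusion of investigational product", with the other two conditions unchanged. The Safety set, defined just above it, reads "Includes all subjects who receive at least one infusion of investigational product, including partial infusions", so the two bullets treat partial infusions differently. SAP 7.5.4.5 then justifies the efficacy set by saying that "this population is the subset of the Safety analysis set who have measurable disease at baseline and have at least one post-baseline on-study assessment" of tumour response; completeness is absent there.

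**Declaration of changes.** SAP section 4 says the SAP overrides the protocol where they differ and that changes of method will be explained. SAP 7.10 names DCR and time to response as additions and continues: "There were no other changes to the study conduct or planned analyses identified within the development of this SAP".

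**Central read.** The primary ORR is by Investigator review. SAP 7.5.2 plans to repeat it with the central read. SAP 7.2 creates a second set for this, requiring a post-baseline assessment based on central data: "This population will be used for the analysis of efficacy data based on central read data only". SAP 7.5.1 confirms that central outputs use it. Section 4 announces this set; 7.10 does not list it.

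**The concern.** The SAP holds two descriptions of its primary denominator, and the stricter one departs from the protocol without being declared. The patients it removes are selected by tolerance of the drug. Protocol 6.6.1 has the infusion stopped for a Grade 3 or 4 reaction. A patient who is never successfully re-treated completes no infusion, yet Protocol Table 2 requires imaging at the EOS visit. With that scan the patient counts as a non-responder under Protocol 9.3 and is left out under SAP 7.2. Protocol 4.5 allows replacement only for non-safety withdrawals, so such a patient is not replaced under that rule. OS is repeated on the Safety set (SAP 7.5.1), but ORR is not, so no planned ORR table brings the patient back.

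The second point concerns interpretation. In an open-label trial with an Investigator-read endpoint, the central read is the independent check on the readers. It is cleanest when both reads cover the same patients. Here a patient with no central post-baseline assessment leaves the central denominator.

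**Working it through.** **1. The plan's own figure.** Inputs from SAP 7.9 and Protocol 9.2: n = 21 then 42, r1 = 2, r2 = 6, response rates 8% and 25%. Success means more than 2 responders of 21 and more than 6 of 42:

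Power = Σ over x = 3 to 21 of P(X₁ = x | 21, 0.25) × P(X₂ ≥ 7 − x | 21, 0.25) = 88.6%.

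The plan states 89.4%, so it reproduces to within a point; the exact type I error is 3.95%. Without the look, which SAP 7.9 says was not conducted, 7 of 42 gives power 92.9% and type I error 4.75%. Seven responders of 42 is therefore the relevant boundary.

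**2. How many patients the word can remove.** A patient is newly excluded only if no infusion was ever completed and a post-baseline scan exists. The documents give no count. The only related rate is in Protocol 1.4.1: a treatment-related anaphylactic reaction of Grade 3 or higher in 1 of 43 patients at 4 mg weekly, or 2.3% (exact 95% CI 0.06% to 12.3%).

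- Expected number: 42 × 1/43 = 0.98; 45 × 1/43 = 1.05.
- Probability of three or more: 7% of the time with 42 patients, 9% with 45.
- Upper confidence limit applied to 45 patients: 45 × 0.123 = 5.5.

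This is an upper guide. It counts reactions, not patients who never completed an infusion and were later scanned.

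**3. Effect on ORR.** Let k be the number of non-responders removed (assumed range 0 to 5), with 7 responders. ORR = 7/(n − k). The one-sided p is P(X ≥ 7 | n − k, 0.08), using the 8% null and the one-sided 5% level in the protocol synopsis.

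| Cohort | k | ORR | one-sided p |
|---|---|---|---|
| 2 (n = 42) | 0 | 16.7% | 0.0475 |
| 2 | 1 | 17.1% | 0.042 |
| 2 | 2 | 17.5% | 0.038 |
| 2 | 5 | 18.9% | 0.026 |
| 1 (n = 45) | 0 | 15.6% | 0.065 |
| 1 | 1 | 15.9% | 0.059 |
| 1 | 2 | 16.3% | 0.053 |
| 1 | 3 | 16.7% | 0.0475 |

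Each excluded patient adds roughly 0.4 points. In Cohort 2, seven responders pass at every k. In Cohort 1, seven would move across 5% only with three exclusions.

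**4. Central denominator.** The counts here are assumptions for illustration. Take 8 local responders of 45 (17.8%), and let the central reader agree on every patient it reads.

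- If 2, 4 or 6 non-responders lack a central assessment: 8/43 = 18.6%, 8/41 = 19.5%, 8/39 = 20.5%.
- If 2 responders lack one: 6/43 = 14.0%.

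Local and central ORR differ in every case although no reading differs, and the sign depends on who is missing.

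**The case against.** The strongest reply is that little is lost. Under Protocol 6.6.1 a Grade 2 reaction can end in a completed infusion. Protocol 7.1.1 provides for re-treatment after Grade 3 or 4, and one later complete infusion qualifies the patient. Patients with no post-baseline scan are excluded by the protocol's own definition. EOS imaging is scheduled, which does not guarantee that it happens. All of this stands and keeps the effect small. A reader might infer that infusion-reaction failures in general drop out of the primary analysis; the documents support that only for the narrow group above.

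A reader might also infer that the SAP hides both changes. It does not: section 4 discloses the central set, and only the completeness condition is undeclared. Nor does the text show that baseline measurability is judged centrally, since the reference to central data follows the post-baseline condition.

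A third tempting reading is that the central ORR is no test of the primary result. That goes too far. SAP 7.5.2 plans side-by-side listings of local and central responses, 7.5.1 lists every exclusion with its reason, and 7.3.1 counts each set. Agreement can be recovered patient by patient; what is missing is a summary of it.

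Finally, one could compare 7/42, with a two-sided 95% lower limit of 7.0%, with 7/36, with a lower limit of 8.2%, and say that losing six non-responders carries the result past the 8% null. The six are not in the documents, and no test of central ORR is planned. At the protocol's one-sided 5% level 7/42 already passes, with a one-sided lower limit of 8.09%.

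A fair objection to the remedy is that counting centrally unread patients as non-responders turns missing scans into apparent disagreement. It does, so that figure is a conservative bound and needs the cross-table beside it.

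**Conclusion.** Two defects hold. First, SAP 7.2 contradicts Protocol 9.3 and SAP 7.5.4.5 on who is in the primary efficacy set, and 7.10 is inaccurate on this item. The likely effect is 0 to 0.4 points of ORR per cohort, assuming that the earlier study's 1/43 is a reasonable upper guide. The direction is realistically upward, since a patient without one complete infusion is very unlikely to respond. The three exclusions that would matter in Cohort 1 are improbable, and the number of affected patients is not documented.

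Second, the central ORR is confounded by a change of patients but remains informative. Neither the size nor the direction of that effect can be derived from the documents. The case for changing both rests on the first touching the primary denominator and on the low cost, not on a demonstrated change in the trial's conclusion.

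**What to change.** 1. In SAP 7.2, in both efficacy sets, replace the completeness condition with *at least one dose, including a partial dose*. This agrees with Protocol 9.3 and SAP 7.5.4.5. If the condition is kept, define it, justify it and declare it in 7.10, and align 7.5.4.5.
2. Report central ORR and DCR also on the primary Efficacy Evaluable set, counting patients not evaluable centrally as non-responders and labelling the result a conservative bound. This parallels the non-responder rule for the primary ORR in SAP 7.5.4.2. Keep the central-evaluable version beside it.
3. Add a cross-table of local by central best overall response, with a category for not evaluable centrally, so that missing reads and reader disagreement can be seen separately.
4. List the central set in 7.10.

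The cost is SAP wording, one extra denominator for two endpoints and one table built from data already due to be listed. No new data are needed. Estimates may come out slightly less favourable.

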#### 4.5 EARLY WITHDRAWAL OF PATIENTS FROM THERAPY OR ASSESSMENT

Patients are free to discontinue their participation in the study at any time and without prejudice to further treatment. The Investigator must withdraw any patient from the study if that patient requests to be withdrawn, or if it is determined that continuing in the study would result in a significant safety risk to the patient.

Discontinuation or interruption of investigational product does not represent withdrawal from the study. Patients may withdraw or be withdrawn from investigational product at any time.

Patients who permanently discontinue investigational product or are withdrawn from the study for non-safety reasons prior to the first efficacy endpoint (i.e., upon 2 cycles of treatment) may be replaced.

Dosing of investigational product must be interrupted for any serious adverse reactions assessed by the investigator as related to investigational product. Restart of dosing may be considered upon approval by the Sponsor's Medical Monitor (or designee) after resolution of IP treatment-related events to baseline.

Please refer to Section [6.6](#) for AL101 dose modifications and toxicity management which may lead to investigational product discontinuation. Pregnancy is a mandatory criterion for permanent discontinuation of investigational product. Any patient being managed with dose interruption for toxicity should have their study assessments followed per SoA.

The patient's participation in the study may be discontinued due to the following reasons:

- Request of Investigator
- Life-threatening event or death
- Patient withdrew consent
- Patient is lost-to-follow-up

The patient may discontinue investigational product due to the following reasons:

- Request of the Investigator
- Adverse event
- Treatment failure
- Patient is non-compliant with study procedures or study protocol

Confidential

Document State: Effective (Controlled)  
CONFIDENTIAL

Page 39 of 118

- Request of Sponsor or regulatory authority
- Pregnancy
- Other (to be specified in the electronic case report form; eCRF)

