### **9.6.2 Efficacy Analysis**

Primary efficacy analysis will be performed on the Efficacy Evaluable set.

The ORR will be estimated based on the proportion of patients with an overall response of either CR or PR, taking into account any requirement for confirmation. Disease response will be assessed using RECIST v1.1 or modified MDA criteria for bone-exclusive disease (see [Table 11](#)). The estimate of the ORR will be accompanied by a 2-sided 95% exact binomial confidence interval (CI) derived using the Clopper-Pearson method.

DOR, PFS, and OS will be summarized descriptively. The censoring rules will be defined in the SAP.

Refer to the SAP for more details.

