7.5 Efficacy Evaluation

7.5.1 *Datasets Analyzed*

All efficacy summaries will be based on the Efficacy Evaluable analysis set (central version for central read outputs) and will be repeated using the PP analysis set for the primary version of each endpoint (the primary version of each endpoint is the first version of the endpoint detailed in each of the sections below, i.e. ORR based on confirmed – local assessment is the primary version of ORR). OS data will also be repeated using the Safety analysis set. A data listing of subjects excluded from any analysis set, to include the reason for exclusion, will be presented.

All efficacy figures will display AL101 4 mg, AL101 6 mg and the total (combined) groups on separate pages.

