7.5.2 Primary Efficacy Endpoint Analysis Methods

The primary efficacy endpoint of objective response rate (ORR) will be performed on the Efficacy Evaluable analysis set in each cohort separately. There will be no adjustment for multiplicity based on the two cohorts, as each cohort is considered an independent trial.

The estimate of the ORR will be accompanied by a 2-sided 95% exact binomial confidence interval (CI) derived using the Clopper-Pearson method.

The following sensitivity analyses will be conducted:

- The primary analysis will be repeated using the PP analysis set;
- The primary analysis will be repeated using unconfirmed response;
- The primary analysis will be repeated using central read based on confirmed response;
- The primary analysis will be repeated using central read based on unconfirmed response.

Maximum percentage decrease from baseline in the sum of tumor diameters will be displayed in a waterfall plot, by patient and cohort, for all Efficacy Evaluable subjects.

The estimate of the ORR and associated 2-sided 95% exact binomial CI will also be summarized in tabular format and using forest plots for the following subgroups:

- Prior systemic therapy (yes vs no);
- Time since last recurrence (< 6 months vs \geq 6 months);

□

- Bone only vs. visceral disease;
- Prior radiation vs. no prior radiation;
- Prior systemic chemotherapy vs no prior systemic chemotherapy.

In addition, the following will be provided for best overall response only (i.e., no other endpoints will have summaries by these subgroups):

- a subgroup analysis of median time on treatment and median time on study by best overall response (assessed by the Investigator and irrespective of confirmation). In addition to the normal summary statistics, Q1 and Q3 will also be displayed on this table.

Listings showing local and central read responses (target, non-target and overall responses for RECIST and overall response by MDA) side by side will be included.

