EORTC QLQ-C30 functional scales (physical, role, emotional, cognitive, and social), symptom scales (fatigue, pain, and nausea and vomiting), global health status / QoL scale, and single items assessing additional symptoms commonly reported by cancer patients (dyspnoea, loss of appetite, insomnia, constipation and diarrhoea and perceived financial impact of the disease) will be summarized using descriptive statistics (mean, SD, median, 25th (Q1) and 75th (Q3) quartiles, and minimum/maximum values). Descriptive statistics will be calculated for observed values and change from baseline at each visit where the EORTC QLQ-C30 is assessed.

7.5.4 *Statistical/Analytical Issues*

7.5.4.1 *Adjustments for Covariates*

No covariate adjustments are planned.

7.5.4.2 *Handling of Dropouts or Missing Data*

The primary analysis of ORR will consider a subject with no evaluable response data to be a non-responder.

Every effort will be made to determine each subject's progression and survival information. However, subjects may withdraw their consent at any time from further participation in the study. Subjects may withdraw consent from treatment, survival follow-up, or both.

In analyses presented over time by visit, no imputations will be performed on missing data. All analyses will be based on observed data only. The effective sample sizes at each assessment visit will be based on the total number of subjects with non-missing data for the parameter of interest at that visit.

Unless otherwise specified, the following general imputation rules will be used for missing data in the assessment of an event:

If all parts of the date are missing, the date will not be imputed. In the case where only the start day of an event is missing, it will be replaced by the start day of study treatment

□

if the event occurs in the same month and year. Otherwise, it will be replaced by the first of the month. If the stop day is missing and the month is equal to the month of the last date of study treatment, the stop day of the event will be replaced by the stop day of study

treatment. Otherwise, the last day of the month will be used to replace the missing stop day.

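### The primary ORR and every planned PFS analysis leave out treated patients who never had a post-baseline scan, and no planned sensitivity analysis brings them back

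*SAP*

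**What the plan says.** Protocol 9.6.2 states "Primary efficacy analysis will be performed on the Efficacy Evaluable set", and SAP 7.5.2 repeats the choice: "The primary efficacy endpoint of objective response rate (ORR) will be performed on the Efficacy Evaluable analysis set in each cohort separately". To enter that set a patient must have measurable disease at baseline and must "have at least one post-baseline on-study assessment of tumor response (based on local, Investigator read data" (SAP 7.2). Protocol 9.3 has the same post-baseline condition. SAP 7.5.4.5 describes the set as the "subset of the Safety analysis set who have measurable disease at baseline and have at least one post-baseline on-study assessment of tumor response".

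SAP 7.5.2 lists four ORR sensitivity analyses: per-protocol, unconfirmed response, central read confirmed, and central read unconfirmed. SAP 7.5.3.2 lists three for PFS: per-protocol, central read, and patients with a best response of PR. For survival, SAP 7.5.1 adds "OS data will also be repeated using the Safety analysis set".

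On missing data, SAP 7.5.4.2 says "The primary analysis of ORR will consider a subject with no evaluable response data to be a non-responder". SAP Table 7 (6.4.1.2), which governs PFS and DOR, treats a death before the first disease assessment as an event on the date of death.

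**The concern.** In a single-arm study summarised by a response proportion, the denominator matters as much as the response count. Patients who stop or die before any scan are unlikely to be a random subset, and none of them can be a responder. Removing them can move the ORR only upwards. The plan uses an all-treated analysis for OS but has none for the primary endpoint.

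PFS has the same gap in a sharper form. The SAP has decided that death before the first assessment is an event, yet it analyses PFS only in patients who had an assessment. Early deaths, which are the least favourable PFS outcomes, drop out of the curve.

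**Working it through.** **1. Which planned analysis can include an unscanned treated patient?**

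| Analysis | Set | Post-baseline scan required? |
|---|---|---|
| Primary ORR, unconfirmed ORR | Efficacy Evaluable | Yes |
| Per-protocol ORR | Subset of Efficacy Evaluable | Yes |
| Central ORR, confirmed and unconfirmed | Efficacy Evaluable (Central) | Yes, on central read |
| PFS: primary, per-protocol, PR subset | Efficacy Evaluable or a subset | Yes |
| PFS: central | Efficacy Evaluable (Central) | Yes, on central read |
| OS on Safety set | All treated | No |

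Only the OS repeat reaches these patients. Since every PFS set requires an assessment, no patient in any of them can die before the first one. The Table 7 row is therefore inoperative.

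**2. Reach of the non-responder rule.** SAP 7.5.4.2 speaks of the primary ORR analysis, which 7.5.2 places on the Efficacy Evaluable set. There it covers patients whose assessments are all not evaluable, a best response that SAP Table 6 provides for. It does not reach a patient outside the set.

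**3. Size of the ORR effect.** With x responders, N treated and k unscanned, the all-treated ORR is x/N and the reported ORR is x/(N−k). The ratio is N/(N−k), or 1/(1−f) with f = k/N:
- f = 5%: 1/0.95 = 1.05
- f = 10%: 1/0.90 = 1.11

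The documents do not give f. For illustration, assume that the planned maxima of 45 and 42 are the treated counts, with 7 responders and 4 unscanned patients per cohort (Clopper-Pearson 95%):

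| Cohort | All treated | Scanned only | Difference |
|---|---|---|---|
| 1 | 7/45 = 15.6% (6.5 to 29.5) | 7/41 = 17.1% (7.2 to 32.1) | +1.5 points |
| 2 | 7/42 = 16.7% (7.0 to 31.4) | 7/38 = 18.4% (7.7 to 34.3) | +1.8 points |

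The difference equals (x/N) × k/(N−k), so it grows with the response rate. With 11 responders it would be 11/41 − 11/45 = 26.8% − 24.4% = 2.4 points in Cohort 1.

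**4. Could it move the reading against the 8% null rate?** With 7 responders the lower 95% limit is 7.96% at n = 37 and 8.19% at n = 36. Passing 8% therefore takes 45 − 36 = 9 exclusions in Cohort 1 or 42 − 36 = 6 in Cohort 2. With 6 responders it is 7.99% at n = 29 and 8.30% at n = 28, so 17 or 14 exclusions. With 8 responders the limit is 8.00% (8/45) or 8.60% (8/42) with none excluded.

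**5. Size of the PFS effect.** If k of N treated patients die before any scan and nobody is censored before the last of those deaths, the all-treated Kaplan-Meier curve from that point equals the scanned-only curve multiplied by (N−k)/N. For k = 4 this is 41/45 = 0.91 or 38/42 = 0.90. Again, k is an assumption.

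The stated Cohort 2 power of 89.4% is not at issue. An exact two-stage calculation (continue with at least 3 responses in 21, succeed with at least 7 in 42) gives 88.6%.

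**The case against.** The case for leaving the plan as it is has real weight. The set was named in advance in both documents, the study is non-comparative, and SAP 7.5.4.4 calls it exploratory. SAP 7.5.2 plans an estimate and an interval, not a test. Set counts (SAP 7.3.1) and the listing of excluded subjects with reasons (7.5.1) would let a reader rebuild the all-treated ORR. Protocol 4.6 and Table 2 call for end-of-study imaging, including after withdrawal, so many early stoppers will have a scan. Early deaths appear in OS on the Safety set. All of this stands, and it keeps the point small. It does not supply a reported all-treated ORR with its interval, nor make the Table 7 row work.

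Several stronger readings are tempting but unsupported:
- **That 7.5.4.2 contradicts 7.2.** It does not: the rule has work to do inside the set (step 2).
- **That 11 of 29 patients were left out.** Protocol 1.3.2 gives 18 evaluable patients at 31 August 2019 and 29 safety patients at 11 October 2019. Enrolment was continuing between those dates, so the gap is not an exclusion rate. The 2 of 29 patients with Grade 5 events are not described as scanned or unscanned. If both were unscanned and nobody else was, the factor would be 29/27 = 1.07.
- **That replacement hides patients.** Protocol 4.5 says those who stop "for non-safety reasons prior to the first efficacy endpoint (i.e., upon 2 cycles of treatment) may be replaced". SAP 7.2 defines its sets by receipt of infusion and makes no exception for replaced patients, so anyone dosed remains in the Safety set.
- **That three exclusions could turn the result.** This needs a one-sided 5% test in Cohort 1 with exactly 7 responders (p = 0.065 at n = 45, 0.053 at n = 43, 0.047 at n = 42). SAP 7.5.2 plans no such test.

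**Conclusion.** The point holds as a low-cost improvement. The direction is certain: for unscanned patients, exclusion leaves the ORR unchanged or raises it, and deaths before any scan are lost from PFS. The size is unknown, may be zero, and is probably small: about 1.5 to 1.8 points of ORR with 7 responders and 4 unscanned patients per cohort. That compares with interval widths of about 23 to 27 points. These figures assume that 45 and 42 are treated counts and that 4 is a plausible number; the documents give neither fact. They do not support a claim that the primary analysis is invalid or that its conclusion would change.

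One related item is housekeeping. SAP 7.2 requires one complete infusion, protocol 9.3 requires one dose, SAP 7.5.4.5 omits the condition, and SAP 7.10 does not declare the difference. It affects only a patient who was scanned but never completed an infusion, so its numerical effect is close to nil.

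**What to change.** Keep the Efficacy Evaluable set as primary, and make these changes:
- **SAP 7.5.2:** add, for each cohort, a sensitivity ORR with Clopper-Pearson interval on the Safety set, counting every subject without an evaluable post-baseline assessment as a non-responder. State that the denominator is all treated subjects, because the default in SAP 7.1.1 ("the denominator to determine the percentage of subjects in each category will be based on the number of subjects with available data") could otherwise remove the same patients again.
- **SAP 7.5.3.2:** add a PFS sensitivity analysis on the Safety set, so that the Table 7 row for death before the first assessment takes effect. State the censoring date for a treated patient who is alive with no post-baseline scan. Table 7 uses the last disease assessment, which for that patient would be the screening scan, before the first infusion.
- **SAP 7.5.4.2:** say in one sentence which subjects the non-responder rule covers.
- **SAP 7.10:** declare the change from one dose to one complete infusion, or align SAP 7.2 with protocol 9.3.

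The cost is two extra tables and a few sentences. No new data are needed and the primary analysis is unchanged. The supportive ORR and PFS may be slightly less favourable than the primary ones.
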